10.4.2 Case Report Form Completion

This protocol will use electronic data capture (EDC) through a qualified third party vendor. The data will be entered in the EDC system in a timely manner on an ongoing basis.

The investigator is responsible for ensuring that data are properly recorded on each patient's case report forms and related documents. An investigator who has signed the protocol signature page should personally sign for the case report forms (as indicated in the case report forms) to ensure that the observations and findings are recorded on the case report forms correctly and completely. The case report forms are to be submitted to Allergan in a timely manner at the completion of the study, or as otherwise specified by Allergan and will be maintained in a central data repository.

10.4.3 Study Summary

An investigator's summary will be provided to Allergan within a short time after the completion of the study, or as designated by Allergan. A summary is also to be provided to the responsible IRB/IEC.

10.4.4 Retention of Documentation

All study related correspondence, patient records, consent forms, patient privacy documentation, records of the distribution and use of all investigational products, and copies of case report forms should be maintained on file.

For countries falling within the scope of the ICH guidelines, the sponsor-specific essential documents should be retained until at least 2 years after the last approval of a marketing application in an ICH region and until there are no pending or contemplated marketing applications in an ICH region or at least 2 years have elapsed since the formal discontinuation of clinical development of the investigational product. These documents should be retained for a longer period, however, if required by the applicable regulatory requirement(s) or if needed by the sponsor.

In addition, for countries not falling within the scope of the ICH guidelines, local regulatory requirements should be followed regarding the retention of clinical study documentation.

Allergan requires that it be notified in writing if the investigator wishes to relinquish ownership of the data so that mutually agreed-upon arrangements can be made for transfer of ownership to a suitably qualified, responsible person.

10.4.4.1 Study Site

The study site should retain the essential documents to be kept at the study site, such as source documents, contracts, informed consent form, protocol, records on control of the investigational product, or other study-related documents until either item 1 or 2 listed below, whichever is later. However, when the sponsor requires that these documents are to be

61

retained for longer period, the study site should discuss it with Allergan about the period and method of preservation. The record retainer designated for each record should be responsible for the preservation.

- 1. The date of approval for manufacturing and marketing applications of the relevant investigational products (in case of discontinuing its development, until at least 3 years after the date of development discontinuation).
- 2. The day at least 3 years after the date of the termination or completion of the clinical study.

The study site and the record retainer should take measures in such a way that these records are not lost or abandoned during the designated period of preservation and that they are presented upon request.

10.4.4.2 Institutional Review Board (IRB)

The IRB should retain all relevant records such as standard operating procedures (SOPs), membership lists (including qualifications of the members), submitted documents, minutes of meetings, and correspondence until either item 1 or 2 listed below, whichever is later.

- 1. The date of approval for manufacturing and marketing applications of the relevant investigational products (in case of discontinuing its development, until at least 3 years after the date of development discontinuation).
- 2. The day at least 3 years after the date of the termination or completion of the clinical study.

When the study site or the sponsor requests the SOPs and membership lists, the IRB should comply with the request.

10.5 Labeling, Packaging, and Return or Disposal of Study Medications/Treatments

10.5.1 Labeling/Packaging

The study medication will be packaged and supplied by Allergan. The medication will be identified as an investigational compound.

The study medication will be provided in sealed study kits containing 2 multi-dose bottles of study treatment; one bottle will be labeled with an and one bottle will be labeled with a

The study number and kit number, at a minimum, will be printed on the outer carton and bottle labels. Additional labeling will be in accordance with local regulations.

10.5.2 Clinical Supply Inventory

The investigator must keep an accurate accounting of the number of investigational units received from Allergan, dispensed or administered to the patients, the number of units returned to the investigator by the patient (if applicable), and the number of units returned to Allergan during and at the completion of the study. A detailed inventory must be completed for the study medication. The study medication must be dispensed or administered only by an appropriately qualified person to patients in the study. The medication is to be used in accordance with the protocol for patients who are under the direct supervision of an investigator. A unit is defined as a study kit that is comprised of 2 multi-dose bottles of study medication.

10.5.3 Return or Disposal of Study Medications/Treatments and/or Supplies

All clinical study medications/treatments and/or supplies will be returned to Allergan or Allergan designee for destruction.

10.6 Monitoring by the Sponsor

A representative of the sponsor will monitor the study on a periodic basis. The determination of the extent and nature of monitoring will be based on considerations such as the objective, purpose, design, complexity, blinding, size, and endpoints of the study.

Authorized representatives of Allergan or regulatory authority representatives will conduct on-site visits to review, audit and copy study-related documents. These representatives will meet with the investigator(s) and appropriate staff at mutually convenient times to discuss study-related data and questions.

10.7 Publications

Allergan, as the sponsor, has proprietary interest in this study. Authorship and manuscript composition will reflect joint cooperation between multiple investigators and sites and Allergan personnel. Authorship will be established prior to the writing of the manuscript. As this study involves multiple centers, no individual publications will be allowed prior to completion of the final report of the multicenter study except as agreed with Allergan.

12.10 Glossary of Abbreviations

Term/Abbreviation Definition 5-HT serotonin

ANCOVA analysis of covariance

AP analysis plan

 AUC_{0-12} area under the curve from time 0 to 12 hours

BID twice daily

bpm beats per minute

C_{max} maximal concentration

C/D cup to disc

cd/m² candelas per square meter
CFR Code of Federal Regulations
CMH Cochran-Mantel-Haenszel

D diopters
DET dry eye test

ECGs electrocardiograms

eCRF electronic case report form
EDC electronic data capture

FDA Food and Drug Administration

GCP Good Clinical Practices
GLP Good Laboratory Practice

HCl hydrochloride

HIPAA Health Insurance Portability and Accountability Act Standards for

Privacy of Individually Identifiable Health Information

ICH International Conference on Harmonisation

IEC Independent Ethics Committee

IOLs intraocular lenses
IOP intraocular pressure

IRB Institutional Review Board IxRS interactive response system

LASIK laser-assisted in situ keratomileusis
MAOIs monoamine oxidase inhibitors

monoamme oxidase minonois

MedDRA Medical Dictionary for Regulatory Activities
mITT modified intent-to-treat

NDA new drug application

NEI VFQ-25 National Eye Institute Visual Function Questionnaire 25

NOAEL no-observed-adverse-effect-level NVPT near vision task-based presbyopia

NZW New Zealand White

OD right eye
OS left eye

OTC over-the-counter
PDE5 phosphodiesterase 5

PGIC Patient Global Impression of Change

PIOL phakic intraocular lens

PP per protocol

PRK photorefractive keratectomy
PRO patient reported outcome

QD once daily

SOP standard operating procedure

UDVA uncorrected distance visual acuity
UNVA uncorrected near visual acuity

US United States

VAS visual analog scale

12.11 Protocol Amendment 1 Summary

Title: A Phase 2, Multicenter, Double-masked, Randomized, Vehicle-Controlled, Study of the Concurrent Use of AGN-190584 and AGN-199201 in Patients With Presbyopia

[figure not shown]
Protocol 199201-009 Amendment 1

Date of Amendment: October 2015

[figure not shown]
Amendment Summary

This summary includes changes made to Protocol 199201-009 (September 2015). The study duration was changed from 47 to 109 to 44 to 117 days, Table 3 was corrected to include the fixed combination of AGN-199201 and AGN-190584 and AGN-190584 and AGN-190584.

12.12 Protocol Amendment 2 Summary

Title: A Phase 2, Multicenter, Double-masked, Randomized, Vehicle-Controlled, Study of the Concurrent Use of AGN-190584 and AGN-199201 in Patients With Presbyopia

Protocol 199201-009 Amendment 2

Date of Amendment: December 2015

Amendment Summary

This summary includes changes made to Protocol 199201-009 Amendment 1 (October 2015). The Allergan Medical Safety Physician contact information was changed and "lot number" was deleted from the description on how study medication will be labeled.

Section	Revision	Rationale
Title Page	The Allergan Medical Safety Physician contact information was changed	To reflect the current physician supporting the protocol
Section 5.5	Study medication will be labeled with medication kit number, study number, and dominant or nondominant eye, and lot number .	Text was revised to match study medication labels

12.13 Protocol Amendment 3 Summary

Title: A Phase 2, Multicenter, Double-masked, Randomized, Vehicle-Controlled, Study of the Concurrent Use of AGN-190584 and AGN-199201 in Patients With Presbyopia

Protocol 199201-009 Amendment 3

Date of Amendment: February 2016

Amendment Summary

[figure not shown]
This summary includes changes made to Protocol 199201-009 Amendment 2 (December 2015). Visit 3 of each dosing period, the OCT measure, and the electrical device PRO measure was removed from the study; the order of the Grand Seiko measurements was reversed to perform UDVA first and then UNVA; and the macroscopic hyperemia assessment was moved to be performed before the slit lamp biomicroscopy.

Section	Revision	Rationale
Title Page	The Allergan Signatory was changed, and an e-mail address was added for serious adverse event reporting	To reflect the current Therapeutic Area Head, and to facilitate serious adverse event reporting
Protocol		

Section

Revision

Rationale

Section 4.5.1.1

If a female becomes pregnant during the study, the investigator will notify the sponsor immediately after the pregnancy is confirmed, and the patient will be exited from the study after appropriate safety follow-up. The investigator will (1) notify the patient's physician that the patient was enrolled in this study and treated with an investigational drug ocular oxymetazoline, ocular pilocarpine, or the combination of oxymetazoline and pilocarpine, and (2) follow the progress of the pregnancy. The investigator must document the outcome of the pregnancy and provide a copy of the documentation to Allergan.

To be consistent with the Informed Consent Form

Section 5.5

The IxRS will provide the site with the specific medication kit number(s) for each randomized patient at the time of randomization. (day 1 of the first dosing period) and on day 1 of each subsequent dosing period.

For clarification

[figure not shown]
Section 5.7

Text referring to a temperature

To apply to sites that may not have a temperature monitoring device

Section	Revision	Rationale
	measurements were added at hours	
Section 8.5	Deleted instruction for patients to remain at the study site for the duration of the visit	To minimize patient inconvenience
Section 8.9	Visit 3/study exit was changed to visit 2/study exit	To reflect the removal of visit 3
Section 9.5	A section on the procedures for pregnancy follow-up and reporting was added	To be consistent with the Informed Consent Form

12.14 Protocol Amendment 4 Summary

[figure not shown]
Title: A Phase 2, Multicenter, Double-masked, Randomized, Vehicle-Controlled, Study of the Concurrent Use of AGN-190584 and AGN-199201 in Patients With Presbyopia

[figure not shown]
Protocol 199201-009 Amendment 4

Date of Amendment: April 2016

Amendment Summary

This summary includes changes made to Protocol 199201-009 Amendment 3 (February 2016). Table 2 and relevant sections of the protocol were corrected to include a photopic pupil measurement (both eyes, distance) at screening and near manifest refraction at baseline/visit 1, and the order of the sodium fluorescein corneal staining (Oxford scale), Schirmer's tear test (with anesthesia), IOP, and gonioscopy/angle assessment was revised for optimal collection during the conduct of the study.

Section Revision Rationale

during the near-vision tasks and associated near-vision task questionnaires, but may use their glasses to fill out other study related questionnaires.

ALLERGAN

Protocol 199201-009 Amd 4

Date (DD/MMM/YYYY)/Time (PT) Signed by: Justification

### 3. List of Abbreviations and Definition of Terms

**Table 3-1 Abbreviations and Definitions of Terms**

Abbreviation/Term	Definition
AE	adverse event
AGN	Allergan
ANCOVA	analysis of covariance
ANOVA	analysis of variance
ATC	Anatomical Therapeutic Chemical
CFB	change from baseline
eCRF	electronic case report form
EO	exploratory objective
GCP	Good Clinical Practice
ICH	International Conference on Harmonisation
LOCF	last observation carried forward
LS	least squares
MedDRA	Medication Dictionary for Regulatory Activities
mITT	modified intent-to-treat
MMRM	mixed-effects model for repeated measures
NEI	national eye institute (NEI) visual function questionnaire - 25 (VFQ-25)
OC	observed cases
PCS	potentially clinically significant
PO	primary objective
PP	per-protocol
PRO	patient reported outcome
PT	preferred term
SAE	serious adverse event
SADE	serious adverse device effect
SAP	statistical analysis plan
SID	subject identification
SO	secondary objective
SOC	system organ class
TEAE	treatment-emergent adverse event
UDVA	uncorrected distance vision acuity
UNVA	uncorrected near vision acuity
VAS	visual analog scale
VFQ-25	visual function questionnaire - 25
WHO	World Health Organization

## 4. Introduction

This statistical analysis plan (SAP) details comprehensive, technical specifications of the statistical analyses of the efficacy and safety data outlined and/or specified in the final protocol of Study 199201-009 (version dated 2015-09-15) and the most recent amendment (version 4 dated 2016-04-04). Specifications of tables, figures, and data listings are contained in a separate document.

This document is organized into 3 main sections:

1. Study overview
2. Statistical Methodology and Study Endpoints
3. Data Handling and Analysis Conventions

[figure not shown]
### 4.1 Study Design Summary

This study is a phase 2b, multicenter, double-masked, parallel-group, randomized sequence, dose response, vehicle-controlled study in patients with presbyopia. Sixteen unfixed combination of AGN-190584 [REDACTED] and AGN-199201 ([REDACTED]) and a fixed combination of AGN-190584 [REDACTED] and AGN-199201 [REDACTED] solutions will be dosed in the nondominant eye during 5 dosing periods. For 17 different treatment combinations, each dosing period will be once daily for 2 consecutive days, followed by a 7 to 21 day washout before the next 2-day dosing period, until exit after the fifth 2-day dosing period. The study duration will be 39 to 112 days per patient.

Following a screening visit (days -18 to -1) patients will be randomized at a baseline visit (visit 1) in a 1:1:1:1 ratio (stratified by uncorrected near vision acuity at baseline of  $\leq 20/80$  and  $> 20/80$ ) to 1 of the following treatment groups:

- Group 1: AGN-199201 [REDACTED] and AGN-190584 vehicle 0%
- Group 2: AGN-199201 [REDACTED] and AGN-190584 ophthalmic solution [REDACTED]
- Group 3: AGN-199201 [REDACTED] and AGN-190584 ophthalmic solution [REDACTED]
- Group 4: AGN-199201 [REDACTED] and AGN-190584 ophthalmic solution [REDACTED]

All patients will receive the fixed combination of AGN-199201 [REDACTED] and AGN-190584 [REDACTED] ophthalmic solutions within one of the 5 dosing periods. Vehicle for AGN-190584, vehicle for AGN-199201, and the vehicle for fixed combination ophthalmic solution have the same formulation.

## 4.2 Study Objectives and Endpoints

Each study primary objective (PO), secondary objective (SO), and exploratory objective (EO) is presented with corresponding endpoint(s) below:

[figure not shown]
**Table 4-1 Study Objectives and Corresponding Endpoints**

[figure not shown]
Objectives	Endpoints
Primary	
PO1 To identify the optimum concentrations of AGN-199201 [REDACTED], [REDACTED] and AGN-190584 [REDACTED], [REDACTED] when dosed in combination once a day for the improvement of uncorrected near vision acuity (UNVA) in patients with presbyopia	The primary efficacy variable is the weighted average change from baseline in UNVA letter in the nondominant eye over 2-day periods between hour 1 and hour 10. Baseline will be the hour 0 measure for each dosing period.

### 4.3

### Schedule of Activities

## 5. Statistical Methodology and Study Endpoints

### 5.1 Statistical Methods Planned in the Protocol and Determination of Sample Size

This statistical analysis plan (SAP) will be approved prior to database lock. The SAP expands the statistical section of the protocol and contains a detailed description of methods to analyze data collected in the study. The text portion of the SAP will be included in the CSR report as Appendix 16.1.9.

#### 5.1.1 Statistical and Analytical Plans

Statistical analyses will be conducted using [REDACTED]

##### 5.1.1.1 Common Conventions

###### 5.1.1.1.1 Analysis Populations

The analysis populations will consist of subjects as defined below:

**Table 5-1 Analysis Populations**

Population	Definition	Study Treatment
Screened	All screened subjects who sign informed consent	—
Modified Intent-to-Treat (mITT)	All randomized subjects with a baseline and at least 1 post baseline assessment of mesopic high contrast UNVA, with baseline vary not more than 3 lines across the 5 dosing period, and will be analyzed as randomized.	Randomized assignment
Per Protocol (PP)	All randomized patients who have no significant protocol deviations that affect the primary efficacy variable and complete all study visits for each dosing period.	Actual received
Safety	All subjects who received $\geq 1$ administration of study treatment	Actual received

[figure not shown]

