1.4 Rationale for Study Design

Allergan Study 199201-007 achieved proof-of-concept for the current approach of treating presbyopia with a combination of oxymetazoline and pilocarpine ophthalmic solutions. This phase 2 clinical study is a systematic dose-response study designed to identify the optimum concentrations of oxymetazoline HCl (0.0125%, 0.05%, or 0.125%) and pilocarpine HCl (0.5%, 1%, or 1.5%) ophthalmic solutions dosed in combination for the improvement of UNVA in patients with presbyopia.

The results from Study 199201-007 suggest that pilocarpine improves UNVA in patients with presbyopia by decreasing pupil diameter which increases depth of focus. Oxymetazoline may further modulate the miotic effect of pilocarpine on UNVA by increasing both accommodation and duration. Study 199201-009 was designed to have more sensitivity to change in oxymetazoline concentration (ie, within patient comparison) than pilocarpine concentration (ie, between patient comparison). Secondarily, the current study brackets the concentration of pilocarpine used in 199201-007, the higher concentration of pilocarpine in the current study may result in a greater discontinuation rate. Thus, pilocarpine was selected as a between-patient variable to minimize any potential impact of patient discontinuation.

This study was designed to dose in the nondominant eye of younger presbyopic patients based on the results of 199201-007, as the greatest improvements in UNVA were seen with these two conditions. Due to the large number of comparisons when crossing over two drugs

each with 3 concentrations as well as monotherapies, it is not practical to use fixed combinations for all dose combinations in the current study. A fixed combination of pilocarpine 1% and oxymetazoline 0.125% was selected as the only fixed combination to enable bridging between the fixed combination used in this study and the unfixed combination used in this study and 199201-007.

Rationale for Dose Range

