5.5 Method for Assignment to Treatment Groups/Randomization

Prior to initiation of study treatment, each patient who provides informed consent will be assigned a patient number that will serve as the patient identification number on all study documents.

[figure not shown]
At the time of randomization on visit 1, eligible patients will be placed into 1 of 2 strata as described in Section 5.4, and they will be assigned to 1 of the 4 treatment groups, in a masked fashion based on the randomization scheme within the patient's stratum according to the order of enrollment. The IxRS will assign the next available randomization number for the appropriate stratum to the patient at the time the investigator requests randomization. The IxRS will report 2 medication kit numbers (one for nondominant eye and one for dominant eye) to use for each patient corresponding to the randomization number. The randomization scheme will be prepared by Allergan Biostatistics.

[figure not shown]
Study medication will be labeled with medication kit number, study number, and dominant or nondominant eye. Each medication kit (carton) will contain 2 multidose bottles of study treatment; 1 bottle will be labeled with an 'X' and 1 bottle will be labeled with a 'Y'. The study treatment in each bottle will be administered in sequence (a single drop from bottle X first, followed 5 to 7 minutes later by a single drop from bottle Y). The IxRS will provide the site with the specific medication kit number(s) for each randomized patient at the time of randomization (day 1 of the first dosing period) and on day 1 of each subsequent dosing period. Sites will assign study medication kits according to the IxRS instructions. Sites will receive the IxRS confirmation notifications for each transaction. All notifications are to be maintained with the study source documents.

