7.1 Analysis Populations

The modified intent-to-treat (mITT) population is defined as all randomized patients with a baseline and at least 1 post baseline assessment of mesopic, high contrast, UNVA and will be analyzed as randomized. The efficacy variables will be analyzed using the mITT population.

[figure not shown]
The per protocol (PP) population is defined as all randomized patients who have no significant protocol deviations that affect the primary efficacy variable and complete all study visits. The PP population will be determined prior to database lock. The primary efficacy variable will also be analyzed using the PP population on an as-treated basis.

The safety population is defined as all patients who received at least 1 dose of study treatment and will be analyzed as treated. All safety measures will be analyzed using the safety population.

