7.2 Collection and Derivation of Primary and Other Efficacy Assessments

7.2.1 Primary Efficacy Variable

The primary efficacy variable is the weighted average change from baseline in UNVA letter in the nondominant eye over 2-day periods between hour 1 and hour 10. Baseline will be the hour 0 measure for each dosing period.

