**Table 5-5 Analysis Population Summaries**

Endpoint	Description	Timing	Methodology
Screened Population	Distribution overall and within countries/regions/sites in total	Screening Period,	Categorical counts

mITT, PP and Safety populations	Distribution overall and within countries/regions/sites in total and by treatment group	Treatment Period	Categorical counts
---------------------------------	---	------------------	--------------------

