### 5.1.1.3 Efficacy Analyses

Efficacy analyses will be based on the mITT Population. The primary efficacy variable, weighted average change from baseline in UNVA letter, will also be analyzed based on the PP population.

The following efficacy assessments are defined:

[Redacted] :

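### The SAP's mITT drops whole patients whose hour-0 UNVA varies by more than 3 lines across periods, so the primary efficacy set is selected partly on the values of post-randomisation baselines, with no readable analysis on the protocol's mITT

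*SAP*

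**What the plan says.** Protocol 7.1 defines the mITT as "all randomized patients with a baseline and at least 1 post baseline assessment of mesopic, high contrast, UNVA and will be analyzed as randomized". It has no condition on how stable the baseline is.

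SAP Table 5-1 starts from the same definition and adds "with baseline vary not more than 3 lines across the 5 dosing period, and will be analyzed as randomized". The condition applies to subjects, not to dosing periods. SAP 5.2.2 lists it among the changes made before database lock. SAP 6.8 gives the reason as correction of a baseline data issue for primary efficacy and does not describe that issue.

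Three other provisions fix what the rule does:

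- Protocol 7.2.1: "Baseline will be the hour 0 measure for each dosing period".
- Protocol 5.5 has kits assigned "at the time of randomization (day 1 of the first dosing period) and on day 1 of each subsequent dosing period", which places randomisation at the start of period 1.
- SAP 5.1.1.3: "Efficacy analyses will be based on the mITT Population". The primary variable is also analysed in the per-protocol set, defined in Table 5-1 as "All randomized patients who have no significant protocol deviations that affect the primary efficacy variable and complete all study visits for each dosing period". That definition has no 3-line rule.

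For reporting, SAP Table 5-5 counts the mITT, PP and Safety populations as "Distribution overall and within countries/regions/sites in total and by treatment group".

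**The concern.** The protocol mITT already requires one post-baseline assessment, so it is not free of post-randomisation information. But it asks only that an assessment exists. The SAP rule selects on the values of later baselines, and those values are the subtracted term in each period's change score.

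The rule can fall unevenly. A patient with one baseline cannot fail it, and the chance of failing rises with each further period attended. Protocol 1.4 compares oxymetazoline within patients and pilocarpine between patients. Dropping a whole patient removes all of that patient's oxymetazoline periods together, so any distortion would fall mainly on the pilocarpine contrast and on who the result applies to.

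The rule is also under-specified. The readable SAP does not say whether variation means highest minus lowest or change from the first baseline, or how the rule treats a patient with fewer than five periods.

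The planned reporting shows the loss only indirectly. Disposition (Table 5-6) and important deviations (Table 5-7) are summarised in the mITT, so removed patients leave those tables too. Table 5-5 allows Safety and mITT counts to be compared, but not by reason or by periods completed.

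**Working it through.** **The plan's own figures.** 4 × 40 = 160 enrolled. At the SAP's 10% dropout, 160 × 0.90 = 144 completers; at the protocol's 12.5%, 160 × 0.875 = 140. Both reproduce. Neither allows for exclusions under this rule. No power, SD or expected exclusion rate is stated.

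**Which values decide membership.** Randomisation is on day 1 of period 1 and baseline is hour 0 of each of five periods. For a completer, 5 − 1 = 4 of the 5 values come after randomisation and after earlier dosing.

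**How many patients noise alone would remove.** The documents give neither a within-patient SD nor the letters per line. Assumptions: 5 letters per line (so 3 lines = 15 letters), independent normal error, no drift, SD 3 to 6 letters. With w = 15/SD and k baselines:

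- Highest minus lowest: P = 1 − k∫φ(x)[Φ(x+w) − Φ(x)]^(k−1) dx
- Change from first baseline: P = 1 − ∫φ(x)[Φ(x+w) − Φ(x−w)]^(k−1) dx

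For whole-letter scoring a patient fails at 16 letters or more; for whole-line scoring, at 4 lines or more. Both are averaged over where the true value lies within a step. Results for k = 5:

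| Reading and scale | SD 3 | SD 4 | SD 5 | SD 6 |
|---|---|---|---|---|
| Highest − lowest, continuous | 0.4% | 6.1% | 21.1% | 39.2% |
| Highest − lowest, whole letters | 0.25% | 4.9% | 18.3% | 35.8% |
| Highest − lowest, whole lines | 0.1% | 2.2% | 10.6% | 24.5% |
| From first, continuous | 0.2% | 2.8% | 10.9% | 22.9% |
| From first, whole letters | 0.1% | 2.2% | 9.3% | 20.5% |
| From first, whole lines | 0.03% | 1.0% | 5.2% | 13.2% |

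At SD 5 the choice of definition roughly halves the loss: 21.1% to 10.9%, 18.3% to 9.3%, or 10.6% to 5.2%.

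**Dependence on periods attended.** At SD 5, whole letters, highest minus lowest, removal with 1, 2, 3, 4 and 5 baselines is 0%, 2.9%, 7.3%, 12.6% and 18.3%.

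**In patients, for the SD 5 case only.** Give each dropout two baselines. In whole letters, highest minus lowest, 140 × 0.1831 + 20 × 0.0285 = 26.2, or 144 × 0.1831 + 16 × 0.0285 = 26.8, of 160. On the change-from-first reading it is about 14. In whole lines the two readings give about 15 to 16 and about 8.

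**Can unequal dropout bias the pilocarpine contrast?** Double one group's dropouts from 5 to 10 of 40, with the same settings: 35 × 0.1831 + 5 × 0.0285 = 6.55 expected removals, against 30 × 0.1831 + 10 × 0.0285 = 5.78. The difference is 0.77 of a patient, so this route is small.

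**The case against.** A reader might infer that the filter biases the treatment comparison, or that it was adopted with knowledge of unmasked results. The documents support neither.

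- The values are pre-dose and follow a washout of 7 to 21 days. Protocol 1.4 reports that in the preceding study pilocarpine's effect had mostly gone by 6 hours and the combination's effect was still present at 6 to 8 hours. Nothing readable suggests carryover a week later. If later baselines do not depend on treatment, the filter costs patients and generalisability but does not distort the contrast. This stands.
- Protocol 1.4 warns that "the higher concentration of pilocarpine in the current study may result in a greater discontinuation rate", which would make the number of baselines differ between groups. The calculation puts that route at about 0.8 of a patient. This also stands.
- The change is disclosed and pre-lock. The readable text does not say whether it was decided under masking, and that silence is not evidence of unmasking.
- The loss rests on assumed SDs, and the documents do not favour SD 5 over SD 3. This stands, so no single figure should be quoted as the trial's loss.
- Parts of SAP 5.1.1.3, Table 5-15, 6.8 and 6.9 are redacted. A definition or an analysis on the protocol mITT could be there.
- Restoring the protocol mITT as primary could return faulty baselines to the change scores, and the nature of the data issue is not visible. This is fair. Which set is labelled primary is open to judgement.

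The per-protocol analysis is a weaker answer. It is free of the 3-line rule but limited to completers without significant deviations, so it does not replace the protocol mITT. As written, a patient could even be in the PP set and outside the mITT.

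**Conclusion.** The point holds as a difference between the current protocol and the current SAP. The primary efficacy set excludes whole patients on the values of baselines mostly taken after randomisation, and the readable text plans no analysis on the set that the protocol defined. The new element is selection on those values, not the use of post-randomisation information as such.

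Bias by treatment is a possibility and is not demonstrated. The likelier cost is fewer patients and a result that applies to people with steady baselines. Because the steadier patients are the ones kept, the restricted estimates may look less noisy than those from the full set.

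The size cannot be derived from the documents. Under the stated assumptions it runs from under 0.1% to about 39% of five-period completers, so it may be negligible or large. The undefined rule alone moves it by about a factor of two at SD 5. It should be fixed, in proportion: the remedy is a second analysis, a definition and a count.

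**What to change.** - In SAP Table 5-1 and 5.1.1.3, add the primary analysis on the protocol 7.1 mITT, reported beside the restricted set, unless redacted text already provides it.
- Define the variation rule (for example, highest minus lowest hour-0 UNVA over attended periods) and state how it applies to patients with fewer than five periods.
- Extend Table 5-5 to show the number excluded by this rule, by treatment group and by periods completed.
- Describe the baseline data issue and use it to justify which set is labelled primary. That choice is the sponsor's. Where a particular hour-0 reading is shown under masking to be erroneous, that patient-period can be set aside with documentation and the patient's other periods kept.

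The cost is SAP wording, one extra run of the primary tables and a slightly larger count table. The protocol-mITT estimates may be noisier, faulty baselines that are not individually identified stay in them, and setting aside single patient-periods slightly unbalances the within-patient oxymetazoline comparison.
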